3.1. Overall Study Design and Plan

This is an open label safety and tolerability extension study for patients who have completed the TR03 study. Patients will either enter directly into a drug Treatment Period (Worst Itch NRS ≥ 5) or enter an extended screening period of a no-drug Observation Period (Worst Itch NRS < 5) based on their reported NRS scores on the first Visit (Visit 1a). For up to 12 extended screening weeks, patients in the no-drug Observation Period may also transition into the drug Treatment Period if their Worst Itch NRS increases to ≥ 5 .

To allow for various starting levels of pruritus intensity, patients who have a Worst Itch NRS that is ≥ 5 will enter the Treatment Period upon completion of Visit 1a. Patients whose Worst Itch NRS score is < 5 will be entered into an extended screening period, no-treatment criteria Observation Period for up to 12 weeks or until they develop a higher level of pruritus (i.e., Worst Itch NRS ≥ 5), at which point they will transition to the Treatment Period upon completion of Visit 1b. All patients entering the Treatment Period, whether immediately upon study entry or following a period of time in the Observation Period, will initially be titrated to a dose that can be as high as 180 mg twice daily (BID) during the first 4 weeks of the Treatment Period. Patients who continue in the Observation Period and maintain a Worst Itch NRS score of < 5 will be screen failed from the study at the end of the 12-week period. For enrolled patients whose Visit 1a worst itch NRS score satisfies the ≥ 5 enrollment criterion and for whom treatment is initiated, the screening visit Visit 1a will also be designated as the baseline visit. For enrolled patients who must continue into the Observation Period, the first visit during that period when the worst itch NRS ≥ 5 criterion is satisfied will be designated as Visit 1b and that visit will serve as the baseline visit.

The total study duration for any individual patient will be up to 53 weeks. For patients who enter directly into the Treatment Period, the total amount of time on drug will not exceed 50 weeks. Patients who enter the Treatment Period from the Observation Period, the total amount of time spent in the combined two periods of the study cannot exceed 50 weeks. All patients who received drug treatment will have a 2-week Washout and Safety Follow-up period at the end of the dosing period, unless consent is withdrawn.

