The total amount of time in the Observation Period cannot exceed 12 weeks. After these 12 extended screening weeks, patients not eligible for the Treatment Period are screen failed from the study. The study periods are summarized below.

Study Period	Study Weeks	Duration
Observation Period	
Patients who do not meet the criteria to start Treatment are followed in Observation Period visits (OV) for up to 12 extended screening weeks. During this time, the patient may meet criteria and become eligible to enter the Treatment Period. If the patient does not meet the criteria to enter the Treatment Period by the end of 12 extended screening weeks (OV12), participation in the study ends and the patient is screen failed
	Up to 12 Extended Screening weeks
Treatment Period	
For patients directly entering the Treatment Period as of Visit 1a, the Treatment Period begins with Study Week 1 (Visit 1a) and ends with Study Week 50.
 
For patients entering the Treatment Period after being followed in the Observation Period, the number of weeks on treatment and the end of the Treatment Period varies. (See Table 8 in the study protocol for the details of which treatment visits are to take place).
 
The End of Treatment Visit will take place after the patient completes the last week of study drug.
	Up to 50 weeks
Washout and Safety Follow-Up Period	
The Washout and Safety Follow-up Period is two (2) weeks in duration.
 
For patients directly entering the Treatment Period as of Visit 1a and completing 50 weeks of study drug treatment, the Washout and Safety Follow-up Period should take place during weeks 51 and 52.
 
For patients entering the Treatment Period after being followed in the Observation Period, the number of weeks on treatment and the end of the Treatment Period varies; Table 8 in the Study Protocol calculates the Treatment Visit assignments for any patient entering the Treatment Period from the respective Observation Period visits. The Washout and Safety Follow-up Period will take place during the two (2) weeks after the patient completes the last week of study drug.
 
The Washout and Safety Follow-up Period Visit will take place in the week following the completion of the two (2) week Washout and Safety Follow-up Period.
	2 weeks

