3.4. Treatments

Following enrollment, the patient will receive 30 mg open-label tablets. At each visit at which study drug is to be dispensed, enough drug should be supplied to ensure a sufficient number of tablets available for dosing until the next visit plus an additional 8 tablets to allow for visit windows and/or possibility of a missed visit.

Study drug can be taken with or without food. Patients will be instructed to take the AM and PM Study Drug tablets at the same times of the day, approximately 12 hours apart, preferably with 240 milliliters (mL) (approximately 8 ounces) of water. If the patient does not take a particular dose at the planned time he or she may take it up to 2 hours later. For example, if a patient is taking the Study Drug at 9 AM and 9 PM but forgets to take the 9 AM dose, the patient may take the 9 AM dose as late as 11 AM. After that time, the patient should skip the 9 AM dose and, instead, take the regularly scheduled next dose at 9 PM.

The first dosing day will be on either Visit 1a or Visit 1b. Titration will be based on tolerability. If the patient is experiencing a study-drug related AE or an AE that may be aggravated by study drug up-titration, the study drug dose should not be increased, regardless of the NRS score.

The Study Drug will be titrated during the Treatment Period Weeks 1 - 4, according to the schedule in Table 3 in the study protocol to a final dose of 30 mg BID up to 180 mg BID. The dosing for Treatment Week 1 is further described in Section 9.6.1 (Visit 1a) and Section 9.6.4 (Visit 1b) of the study protocol. Patients should only ever be dispensed a single strength of the study drug (e.g. 30 mg bottle(s) or 60 mg bottle(s)) at a visit.

Patients will titrate to tolerability beginning with a 30 mg dose on Day 1 (Visit 1a or Visit 1b) with a dose increase of 30 mg BID not more often than every 3 to 4 days in order to attain steady-state plasma concentrations of nalbuphine at each dose.

Patients should be instructed to up-titrate beginning with a single 30 mg dose in the evening (PM) and then begin dosing with an increased 30 mg BID dose the following day. Dose titrations should be maintained for 3-4 days before further up-titration of the patient's dose is attempted

The maximum dose the patient should reach at the end of Week 1 is 60 mg BID. If this dose is tolerated (as determined by the Telephone Contact 1 (TC1) assessment), an additional up-titration may be attempted during Week 2.

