7.1. Concomitant Medications

Patients may receive all clinically indicated medications during the study with the exceptions noted in the study protocol.

A medication's usage will be considered concomitant if it was used by the patient at the time of informed consent or started and/or continued after administration of the study medication.

Concomitant medications, including over-the-counter medications, nutritional supplements, and vitamins will be coded according to the World Health Organization (WHO) Drug Dictionary.

For the purpose of summarizing prior and concomitant medications, incomplete medication start and end dates for medications which are not ongoing will be imputed as follows:

- If the year and month are present and the day is missing, then the day is set to the first day of the month for the start date, and to the last day of the month for the end date.
- If the year and day are present and the month is missing, then the month is set to January for the start date, and to December for the end date.
- If the year is present and the month and day are missing, then the month and day are set to January 1 for the start date, and to December 31 for the end date.
- Data listings will include the recorded and imputed (as described above) start and end dates for each reported medication.

If the medication start date is completely missing and the end date is after the first dose of study drug, then the medication will be classified as concomitant. If the end date is missing, then the medication will be classified as ongoing (concomitant). Medications for which the start and end dates are missing will be classified as concomitant.

The total number of concomitant medications and the number and percentage of patients using at least one concomitant medication will be summarized overall for the safety population.

The number and percentage of all concomitant medications will be summarized by Anatomic and Therapeutic Class (ATC) of WHO drug and preferred term overall for the safety population. Patients will be counted only once within a medication category. If a patient reports taking the same medication more than once, as determined by WHO Drug name, then the medication will be counted only once for that WHO Drug name and patient.

Concomitant medications will be presented in a data listing for the safety population.

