Opioid medication usage is summarized and listed with all other concomitant medications. Rescue medications, as described in Section [7.2](#), will be summarized and listed separately from concomitant medications.

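### SAP Section 7.1 lets use at informed consent alone make a drug concomitant, so drugs stopped in the Observation Period before any nalbuphine can enter the concomitant summary (minor)

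*SAP*

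**What the plan says.** Section 7.1 of the SAP classes a medication as concomitant by either of two conditions. The first: "A medication's usage will be considered concomitant if it was used by the patient at the time of informed consent". The second, joined to it by an alternative: "or started and/or continued after administration of the study medication". Either is enough.

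The same section then handles incomplete dates. Where no start date is known, the condition for the concomitant class is different: "If the medication start date is completely missing and the end date is after the first dose of study drug". A missing end date means ongoing, hence concomitant, and a record with neither date is also concomitant. The date-imputation paragraph is introduced as serving both prior and concomitant medications, but the section gives no definition of prior and plans no display for it.

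The interval between consent and first dose depends on the entry route. Section 3.4 says "The first dosing day will be on either Visit 1a or Visit 1b". Patients below the itch threshold at Visit 1a first go, under Section 3.1, into a "no-treatment criteria Observation Period for up to 12 weeks", and the same section confirms the ceiling: "The total amount of time in the Observation Period cannot exceed 12 weeks".

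The summary is made for the Safety population, which Section 4.6.2 treats as one nalbuphine group. On opioids, Section 7.1 says "Opioid medication usage is summarized and listed with all other concomitant medications". Rescue anti-pruritic drugs are summarised and listed apart from this table (Sections 7.1 and 7.2).

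**The concern.** A concomitant-medication table in a safety extension is read as a description of what patients took together with study drug. The consent condition admits drugs that were never taken together with it. For direct entrants this hardly matters if consent and first dose both fall at Visit 1a. For Observation Period entrants the two dates can be weeks apart, so the same table mixes true co-medication with medication that had already ended.

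The rule is also uneven within the Observation Period. Whether a drug that ended before dosing is counted depends on whether it happened to be in use on the consent day, not on how close it came to nalbuphine. And it differs from the anchor used for other summaries in the SAP: Baseline (Section 4.2), treatment-emergent adverse events (Section 9.1) and the rescue-medication totals (Section 7.2) are all set by the first dose in the extension study, and days of rescue use are split at first dose (Section 8.5).

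At stake is the correctness of counts in one planned Safety-population summary. No endpoint is computed from it.

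**Working it through.** The SAP gives no figure on this point to reproduce. The check applies the Section 7.1 rule to example dates and compares it with a plain overlap rule.

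**Inputs**
- Consent = day 0. Assumption: consent is given at Visit 1a; the SAP does not state the day.
- Longest Observation Period: 12 weeks (Section 3.1), so 12 × 7 = 84 days.
- First dose on day D, with D = 0 (direct entrant), 28 (an intermediate example) or 84 (the maximum).
- SAP rule with a known start: concomitant if in use on day 0, or started on or after D, or still in use on or after D.
- SAP rule with the start missing: concomitant if the end date is after D or is missing.
- Overlap rule: concomitant if ongoing, or if the end date is on or after D.
- Days from stop to first dose = D − end day.

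**Results for D = 84**

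| Drug | Start | End | Stop to first dose | SAP 7.1 | Overlap |
|---|---|---|---|---|---|
| A. In use at consent, stopped at once | day −30 | day 1 | 84 − 1 = 83 days | concomitant | no |
| B. In use at consent, stopped late | day −30 | day 83 | 84 − 83 = 1 day | concomitant | no |
| C. Started after consent, stopped late | day 1 | day 83 | 84 − 83 = 1 day | not concomitant | no |
| D. Start unknown, stopped early | missing | day 1 | 84 − 1 = 83 days | not made concomitant by any rule | no |
| E. Continues across first dose | day −30 | day 94 | overlaps | concomitant | yes |
| F. New on treatment | day 87 | day 93 | overlaps | concomitant | yes |

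Three comparisons follow.
1. A against C: the drug that ended 83 days before nalbuphine is counted; the one that ended 1 day before is not.
2. B against C: the same stop date gives different classes.
3. A against D: the same stop date again, but D meets no stated condition for the concomitant class and there is no prior class to receive it. It is left unclassified.

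Read strictly, the missing-start rule also asks for an end date later than the first dose, so an end date on the dosing day itself is not covered either.

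**Other values of D.** With D = 28, a drug in use at consent and stopped on day 1 is still counted, 28 − 1 = 27 days before dosing. With D = 0 the SAP rule and the overlap rule agree in every example tried.

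**Direction of the error.** Rows E and F show that drugs truly taken with nalbuphine are captured either way. The disagreement is in rows A and B: extra drugs, all from patients whose first dose came after the consent day.

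**The case against.** The strongest reply is that overlap is already in the definition. A reader who stops after "considered concomitant if it was used by the patient at the time of informed consent" might infer that the SAP defines concomitant use by consent instead of by overlap. It does not: the sentence goes on to a second condition covering drugs started or continued after dosing. This stands, and it limits the point to over-inclusion.

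Second, the table is not the sole record. The listing carries recorded and imputed start and end dates, so a drug that ended before dosing can be identified. Rescue drugs are summarised apart, with totals restricted to use after first dose and days of use split at first dose. This also stands. It makes the extra entries traceable but does not correct the summary counts.

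Third, a reader might infer that adverse events will be interpreted against the wrong background medication, or that opioid co-exposure in particular will be overstated. The SAP supports neither. It plans no analysis of adverse events by concomitant medication, and all summaries are descriptive. Tabulating opioids with other drugs is a declared change (Section 4.11), and nothing in the document shows that any patient would be using an opioid at consent and stop it before first dose. Opioids fall under the same rule as any other drug in this table, and no more than that can be said.

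Fourth, the missing-start rule need not be a rival definition. When the start is unknown, use at consent cannot be shown from the dates, so the rule falls back on the second condition. That is fair, but the unclassified case (row D) remains.

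Finally, other windows in the SAP also open at consent, namely adverse-event recording (Section 9.1) and the denominator for percentage of time on rescue (Section 8.5). Yet adverse events recorded from consent are still divided at first dose before they are summarised as treatment-emergent. The concomitant table has no such division.

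**Conclusion.** The point holds as a minor definitional fault. Followed as written, Section 7.1 places in the concomitant summary any non-rescue drug in use on the consent day, even if it ended before the first dose of nalbuphine. The interval can reach 84 days for a patient who uses the full Observation Period. That figure assumes consent at Visit 1a; earlier consent would lengthen it and could open a gap for direct entrants too.

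The scope is narrow. Only drugs in use on the consent day are affected, not everything stopped during Observation. A drug stopped and later resumed on treatment adds no false count, because each drug name is counted once per patient.

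A reader might want a percentage of patients affected. The SAP gives neither the share of Safety patients who enter through Observation nor the share who stop a drug before dosing, so any such figure would rest wholly on assumed inputs. The size is not estimable from the document.

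**What to change.** In Section 7.1, replace the two-part definition with one anchored on first dose in TR03ext. Suggested text: *A medication is concomitant if any use occurred on or after the date of first dose in TR03ext, that is, if it is ongoing or its end date, after the stated imputation, is on or after that date. A medication is prior if its end date, after imputation, is before that date.*

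Then:
- Drop the consent condition.
- Use the same anchor in the missing-date rules, so that a missing start with an end date on or after first dose is concomitant, and with an earlier end date is prior. Keep the existing treatment of missing end dates.
- Show medications that ended before first dose in a prior-medication row or listing, so that use during the Observation Period stays visible.
- If the protocol carries the consent wording, record the change in Section 4.11.

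The cost is a short definition, one derived flag, and one extra row or listing. It needs no new data and changes nothing in patient management.

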7.2. Rescue Anti-Pruritic Medications

Rescue medications will be defined as those drugs, when used for the purpose of treating itch, that were required to be washed out prior to entry into TR03 as described in the protocol. For the purposes of this study, any ultraviolet (UV) light treatment received will also be defined as a rescue medication. If a medication is prescribed for chronic anti-pruritic use of greater than 2 weeks, the patient should be discontinued as described in the protocol.

Concomitant use of medications for pruritus is not prohibited except as described in the protocol. Details pertaining to the use of opiate medications are also discussed in the protocol. The list of protocol-defined rescue medications for itching is presented in [Table 1](#).

For drugs that may be used for multiple indications including pruritus, a drug is only considered a rescue medication if taken for pruritus. Use of rescue medications will not preclude continuation in the study; however, all uses of such medication along with their indication for use will be recorded. Patients will be provided a log on which to record use of rescue medications.

Table 1: List of Rescue Medications for Itching

Table 1: Rescue Medications for Itching		
Rescue Medication	Only intended for anti-pruritic treatment	Examples
Opioid receptor antagonists		naltrexone, naloxone
Antihistamines	✓	topical or systemic
Topical calcineurin inhibitors	✓	tacrolimus
Topical antibiotics	✓	---
Topical steroids	✓	---
Topical capsaicin	✓	---
Anti-septic baths and anti-septic cleansing lotions	✓	---
Anti-convulsant class drugs	✓	gabapentin or pregabalin
Systemic Steroids	✓	---
cyclosporin A and other immunosuppressants	✓	---
antidepressant medications	✓	paroxetine, fluvoxamine, amitriptyline
Malignant tumor related active treatment with a systemic drug	✓	---
UV Therapy	✓	---

The total number of rescue medications subsequent to the first dose of treatment with study medication and the number and percentage of patients using at least one rescue medication subsequent to the first dose of treatment with study medication will be summarized overall for the safety population.

Incidence of concomitant rescue medication use will be summarized for the safety population. For incidence of use, patients will be counted only once within a medication category. In addition, for incidence of use calculations, if a patient reports taking the same medication more than once, as determined by WHO Drug name, then the medication will be counted only once (incidence of use) for that WHO Drug/medication name and patient.

The prevalence of use of rescue medications will also be summarized for rescue medications for the safety population. In this construct, multiple, distinct instances when a particular rescue medication was required will be counted as the number of times reported.

Antihistamine use across ATC classifications (a list to be furnished prior to data base lock) will also be summarized by incidence and prevalence for the safety population.

Rescue medication use will be presented separately in a data listing for the safety population.

The number and proportion of patients with rescue medication use at each visit and within ATC classification will be presented. This will be obtained by comparing the rescue medication onset date to the patient's visit dates and slotting the rescue medication accordingly. The number of days of rescue medication use will also be evaluated using descriptive statistics. Details regarding the analysis of number of days of rescue medication use are presented in Section [8.5](#).

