3.2. Premature Discontinuation of Study Drug Treatment

3.2.1. Premature Discontinuation of Study Drug Treatment Associated with Failure-to-Improve Criterion

Patients who meet failure-to-improve criterion during the conduct of the study, will stop taking study medication.

The Failure-to-Improve criteria are as follows: Beginning on Treatment Period Visit 3 (TV3), and at every subsequent Treatment visit, patients with a worst itch NRS score \geq the worst itch NRS score at Visit 1a (or at Visit 1b in the case of patients who require the OV period) will be discontinued from study drug. Patients discontinued from study drug are to undergo the End of Treatment Visit (TV14), the Washout/Safety Follow-up Period assessment in two weeks, and receive a follow-up telephone contact 30 days following end of study drug dosing for final safety assessment.

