8.2. Change during the Washout Period in PROs

Change during the Washout Period after cessation of treatment in the following PROs will be summarized using simple summary statistics generated for the End of Treatment visit and the Washout/Safety Follow-up visit and for change from the End of Treatment visit to the Washout/Safety Follow-up Visit.

- Worst itch intensity NRS
- Average itch intensity NRS
- VRS (itchy, burning, stinging)
- ItchyQoL Total Score
- MOS Sleep Scale-R Question 2
- HADS

No formal analysis of this presentation of data will be performed. Note that only patients who complete the study through the End of Treatment visit will be included in this evaluation.

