8.5. Rescue Medication Use

Details regarding the definition of and overall summary of rescue medications are presented in Section [7.2](#).

The number of days of use of rescue medications by study period (Pre-Treatment (after the date of last visit during the TR03 core study and prior to first dose during the TR03 extension study) and Treatment Period (Visits 2-14)) and by visit for the Treatment Period will be summarized

using descriptive statistics for both the overall number of days of use as well as for the number of days of rescue medication use for the drug classes presented in [Table 1](#).

The number of days of rescue medication use between each visit will be presented graphically for overall rescue medication use as well as for each of the drug classes presented in [Table 1](#).

The overall number of days of rescue medication use and number of days of rescue medication use for each of the drug classes presented in [Table 1](#) will be summarized using descriptive statistics. For patients with ≥ 1 day of rescue medication use, percentage of total time on study will be derived as: $[(\text{the number of days of rescue medication use})/(\text{days from the informed consent date through the fixed dose period})] * 100$. The mean for all patients on-study during the time period will be presented.

Time to first new use of rescue medication (days) will be summarized using descriptive statistics. The earliest date on or after the date of first dose of study medication on which a patient begins new rescue medication use will be considered the date of first new use of rescue medication. Time to first new rescue medication use will be derived as: $(\text{date of first new use of rescue medication} - \text{date of first dose of study medication}) + 1$. For patients who have no new rescue medication use on or after the date of their first dose of study medication time to first new use of rescue medication is not calculated.

It is recognized, however, that all of these evaluations are potentially confounded with early discontinuation that may or may not be observed among patients reporting use of rescue medications. That is, the extent and duration of use of rescue medications may, at least in part, be a function of duration of participation in the study.

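### Rescue incidence and time to first new rescue use have no end at last dose, so off-drug Washout starts are pooled with on-drug use, while the days-of-use periods stop at Visit 14

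*SAP*

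**What the plan says.** Section 3.3.2 lists time to first use of rescue medication and number of days of use as a secondary endpoint. The SAP summarises rescue use over several windows:

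- **Overall count and incidence (7.2).** The total number of rescue medications and the number and percentage of "patients using at least one rescue medication subsequent to the first dose of treatment with study medication". A start is given, but no end.
- **Time to first new use (8.5).** The event date is "The earliest date on or after the date of first dose of study medication on which a patient begins new rescue medication use". Again there is a start and no end. For patients without such a date, "time to first new use of rescue medication is not calculated".
- **Days of use by period (8.5).** "The number of days of use of rescue medications by study period (Pre-Treatment" is followed by a second and last period, "Treatment Period (Visits 2-14)) and by visit for the Treatment Period will be summarized". No Washout period is named.
- **Percentage of time (8.5).** The numerator is days of rescue use with no stated end. The denominator runs from informed consent through the fixed dose period.
- **By-visit table and listing (7.2).** Patients with use are tabulated at each visit, slotted by onset date against visit dates, and all rescue use is listed.

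Section 3.1 gives all treated patients a two-week Washout after dosing unless consent is withdrawn. Section 3.2 applies this to early stoppers as well: "Patients discontinued from study drug are to undergo the End of Treatment Visit (TV14), the Washout/Safety Follow-up Period assessment in two weeks". Section 4.6.2 puts everyone in one nalbuphine group.

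**The concern.** Read literally, a rescue drug begun after nalbuphine has stopped counts the same as one begun while the patient was taking it. The patients most exposed to this are plausibly those stopped for failure to improve. Under 3.2.1 their worst itch NRS is at or above its baseline value, and 3.1 required a baseline of at least 5 to start treatment, so they enter the Washout with substantial itch.

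Two things are at stake. First, a listed secondary endpoint mixes on-drug and off-drug use, and a reader of the report could not tell from the headline incidence how much is which. Second, the rescue summaries do not agree with one another: the same Washout start is inside the incidence and the time to first use, outside both days-of-use periods, and undefined in the percentage-of-time formula.

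**Working it through.** The SAP states no rescue rate, discontinuation rate or sample size (4.3 says the size cannot be predicted), so there is no planned figure to reproduce. The check has three parts.

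**1. One event followed through each summary.** Take a patient whose first rescue drug starts in the Washout.

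| Summary | Section | Is the Washout start included? |
|---|---|---|
| Overall count and incidence | 7.2 | Yes, no closing date |
| Time to first new use | 8.5 | Yes, no closing date |
| Days of use by period | 8.5 | No, periods are Pre-Treatment and Visits 2-14 |
| Percentage of time | 8.5 | Numerator open; denominator ends with the fixed dose period |
| By-visit table | 7.2 | Possibly; the Washout visit is not named as a row |
| Listing | 7.2 | Yes |

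**2. Share of the window that is off drug.** Inputs: Washout of 14 days (3.1); maximum of 350 days on drug (50 weeks, 3.1); failure-to-improve stops begin at TV3 (3.2.1), which is Visit 3/Week 5 (7.3.1), so about 28 days on drug. The 84- and 182-day rows are intermediate examples. The formula is 14 / (days on drug + 14).

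- 28 days: 14/42 = 33.3%
- 84 days: 14/98 = 14.3%
- 182 days: 14/196 = 7.1%
- 350 days: 14/364 = 3.8%

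The Washout visit falls in the week after the two weeks end (3.1), so 14 days is the least the off-drug window can be.

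**3. Effect on the reported results.** Let p be the true proportion with rescue use on drug and q the proportion of the remaining patients who start rescue in the Washout. Reported incidence = p + (1 − p) × q. Both inputs are assumptions.

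| p | q = 5% | q = 10% | q = 20% |
|---|---|---|---|
| 20% | 24.0% | 28.0% | 36.0% |
| 30% | 33.5% | 37.0% | 44.0% |
| 50% | 52.5% | 55.0% | 60.0% |

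For example, 0.20 + 0.80 × 0.05 = 0.24 and 0.20 + 0.80 × 0.20 = 0.36. The open window can only raise the incidence.

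Time to first use can move either way. By the 8.5 formula, a patient with last dose on day 28 who starts rescue on day 29 gets (29 − 1) + 1 = 29 days, with no use on drug. A completer who starts in the Washout, dated by the 9.1 window of first dose + 350 to first dose + 363 days, gets 351 to 364 days. If the window closed at last dose, neither patient would have a time calculated.

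**The case against.** The strongest reply is that the plan is less silent about the Washout than this suggests.

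- **Visibility.** A reader might infer that Washout rescue is never shown. The SAP does not support that. The 7.2 table covers use at each visit by onset date and is not limited to Treatment Period visits, whereas 8.1, 8.3 and 8.6 say so when they mean that limit. In 8.1.8 the same phrase needs a note that the PAS is not done at the Washout visit, which suggests it would otherwise reach that visit. The 8.5 graph of days between visits may also extend there, and the listing gives all use. What stands is that the SAP does not say whether the Washout visit is a row.
- **Labelling.** A reader might infer that the SAP presents the count as use on nalbuphine. Its label is use after first dose, and the endpoint in 3.3.2 carries no on-drug restriction. Rescue begun just after stopping for failure to improve is informative and should not be lost. That argues for showing it separately.
- **Washout PRO change (8.2).** A reader might infer that early stoppers treated in the Washout distort this summary: "Change during the Washout Period after cessation of treatment in the following PROs will be summarized using simple summary statistics". But 8.2 includes only patients who complete through the End of Treatment visit. Since early stoppers also attend a TV14 visit, the restriction can be read two ways, but on its natural reading they are excluded. Completers could still start rescue.
- **Size.** Much larger inflation can be produced by assuming high Washout start rates, but nothing in the document supports any particular rate. Whether and how anti-itch treatment may start in the Washout is left to the protocol, which is not at hand.

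The caveat that closes 8.5 does not answer the point. It says that rescue use depends on duration of participation and does not address use after the drug has stopped.

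**Conclusion.** The point holds in this form: overall rescue incidence and time to first new use open at first dose and do not close at last dose, while the days-of-use periods end at "Treatment Period (Visits 2-14") and the percentage formula has an open numerator over a closed denominator. On-drug and off-drug use are therefore pooled in some summaries and not in others.

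The window arithmetic, about 3.8% off drug for a 50-week completer and about 33% for a patient stopped near day 28, rests on durations in the SAP. The incidence illustration of 20% becoming 24% to 36% rests on assumed rates and should not be read as an estimate. The study is open-label, single-group and descriptive, and the primary safety endpoint is untouched. Even so, the choice of window changes the reported values of a listed secondary endpoint, so it should be settled before database lock. The SAP already separates the Washout for adverse events (9.1.1, 9.1.3, 9.1.5) and for discontinuations (8.6); the rescue sections are out of line with that practice.

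**What to change.** 1. In 7.2 and 8.5, define on-treatment rescue incidence, prevalence and first new use as starts from first dose through last dose of study drug.
2. Add the Washout, from the day after last dose to the Washout visit, as a separate period in the incidence and days-of-use tables, and name the Washout visit as a row in the by-visit table.
3. In the percentage-of-time formula, use the same start and end dates for numerator and denominator.
4. Optionally, flag in 8.2 the included patients who started rescue after last dose, keeping the stated restriction to those who complete through the End of Treatment visit.

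The cost is SAP wording, one extra column and some small cells. No new data are needed: medication dates are handled in 7.1 and the last-dose date in 7.3.2. One detail needs care. The 7.1 rule sets a missing start day to the first of the month, which could move a Washout start back before last dose, so the text should say how such partial dates are assigned. No information is lost, because starts after last dose move to their own period.
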